All AEs and medications will be recorded from signing of the informed consent form to Day 29. Thereafter to the end of the study, only MAEs, NCIs, SAEs, immunosuppressive medications (see list in Appendix 3), and vaccines will be recorded. Samples for clinical laboratory tests (hematology, serum chemistry, urinalysis) will be collected at Screening and on Days 8 and 29. A complete physical examination and vital signs will be performed at Screening and predose on Day 1, and targeted and symptom-driven physical examinations will be performed and vital signs measured 2 hours postdose and on Days 4, 8, 15, and 29. An electrocardiogram (ECG) will be performed at Screening and on Day 29. If a subject experiences acute symptoms compatible with adenoviral infection within 28 days after the NasoVAX/placebo dose, a sample will be collected for viral culture as clinically indicated.

One interim analysis of humoral immunogenicity data and safety data (including summaries of AE, reactogenicity, concomitant medications and vaccines, vital signs, ECG, and laboratory data and listing of any viral culture results) will be conducted when all data through the Day 29 visit is available and monitored for all subjects.

A complete schedule of procedures and assessments for study ALT-103-201 is in Table 4-2.

ALT-FLZ-401, Extent and Durability of Immune Response Following Seasonal Influenza Vaccination in Healthy Volunteers, was an open label study designed to generate an immunogenicity sample set similar to that of ALT-103-201 in subjects receiving a licensed influenza vaccine based on the same H1 strain (A/California 2009). The seasonal vaccine H1 component changed at the time of the ALT-103-201 study to A/Michigan, so it was logistically much easier to conduct this study non-contemporaneously with the seasonal vaccine licensed for use in 2016-17. The same site, entry criteria and schedule of assessments for immunogenicity were followed. Twenty subjects were enrolled and samples from this study were frozen and stored and then shipped to blinded laboratory for immunogenicity testing in parallel to the samples from ALT-103-201. The schedule of events for ALT-FLZ-401 is in Table 4-3.

Table 4-2. ALT-103-201 TIME AND EVENTS SCHEDULE

Study Visit	Screening	Dosing Period							Follow-up Period	
		Day 1		Day 2 ^a	Day 4	Day 8	Day 15	Day 29	Day 91	Day 181
Window (days)	Day -28 to Day -1	Predose	Postdose		± 1	± 1	± 1	± 3	± 10	± 10
Informed consent	X									
Demographics	X									

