Nasopharyngeal swab		X				X		
Prior/Concomitant medications	X	X	X	X	X	X	X	X
Adverse Events ^f		X	X	X	X	X	X	X

^a All vital signs (BP, pulse rate, and body temperature) will be measured at Screening in the supine position. On Day 1, temperature, blood pressure and pulse rate will be assessed.

^b See Section 10.5 for listing of tests

^c Opiates, benzodiazepines, amphetamines, cocaine, barbiturates, phencyclidine

^d At Screening and Day 1 WOCBP must have negative urine pregnancy test results

^e Review inclusion/exclusion criteria and may also include a limited physical examination

^f Any subject that experiences an AE (whether serious or non-serious) or has clinically significant abnormal laboratory tests will be followed until resolution or clinical stability up to 180 days after administration of the vaccine or longer if specified by the Investigator.

^g ET= early termination for any subject that discontinues prior to Day 29 visit, ET occurs after Day 29, the procedures for Day 181 will be followed.

^h Height and weight are not required at Day 1

SUMMIT ANALYTICAL

5 Analysis Populations

The following analysis populations will be used:

- **Safety Population:** All ALT-103-201 and ALT-FLZ-401 subjects who provide informed consent, are randomized, and receive at least 1 vaccination. The Safety Population will be used for all safety analyses and will be analyzed according to the treatment received.
- **Intent-to-treat (ITT) Population:** All ALT-103-201 and ALT-FLZ-401 subjects in the Safety Population who have HAI assay results on Day 1 and any postvaccination time point. The ITT Population is the secondary population for immunogenicity analyses. Analyses based on the ITT Population will be undertaken and presented only if >5% of subjects in any 1 dose group are excluded from the per-protocol population. The ITT population will be analyzed according to treatment as randomized.

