- **Per-protocol (PP) Population:** All ALT-103-201 subjects in the Safety Population that received the assigned dose of the test article in accordance with the protocol; have HAI assay results on Days 1 and 29; and had no major protocol deviations affecting the primary immunogenicity outcomes as determined by the Sponsor prior to database lock. ALT-FLZ-401 subjects are included if they received the assigned dose of the test article in accordance with the protocol and have HAI assay results on Days 1 and 29. The PP Population is the primary population for immunogenicity analyses and will be presented regardless of whether subjects are excluded. The PP population will be analyzed as randomized.

SUMMIT ANALYTICAL

6 Analysis Variables

In what follows, variables to be analyzed have been grouped under the headings 6.1 to 6.4. Additional variables may be added as further drafts of the eCRF and this SAP are developed and/or as discussion unfolds concerning the usefulness of *derived* variables formulated using the information presented below.

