8.6 Immunogenicity Analysis

All immunogenicity analyses will be conducted on the PP Population. Analyses based on the ITT Population will be undertaken and presented only if >5% of subjects in any 1 dose group were excluded from the PP Population. Summaries and analysis will be completed by dose group and overall for subjects on an active NasoVAX dose.

The variables that will be analyzed, and the endpoints generated for each variable, are listed in Table 8-1:

Table 8-1. Immunogenicity Variables and Endpoints

Variable Name	GMT	GMR	SPR	SCR	Responder Rate	Geometric Mean SFUs	Compare to ALT-FLZ-401
A/California 2009 antibody level measured by HAI in serum	X	X	X	X			X
A/California 2009 antibody level measured by MN in serum	X	X			X		X
Cellular response to A/California 2009 peptides measured by enzyme-linked ELISpot in PBMCs					X	X	X
IgA antibody level measured by ELISA in nasopharyngeal swab	X	X					X
Antibody level measured by HAI in serum against the following nonrepresented strains: - A/Brisbane/59/2007 (H1 strain) - A/Saint-Petersburg/61/2015 (H1 strain) - A/New Jersey/76 (H1 strain) - A/Perth/16/2009 (H3 strain) - A/Vietnam/1203/2004XPR8 (H5 strain)	X	X			X		X
Antibody level measured by MN in serum against nonrepresented strains	X	X			X		X
Ad5 antibody levels in serum	X	X			X		

Note: Refer to Section 3 for descriptions of each endpoint.

Assay data will be tabulated by visit using the applicable endpoint(s) (e.g., GMT, GMR, or geometric mean SFUs) and their 95% CIs. Graphical representations of the longitudinal immune responses will also be given.

[figure not shown]
Analysis of covariance (ANCOVA) will be used in the analysis of the antibody levels at each post-baseline visit, with log-transformed antibody level as dependent variable, dose group as a factor, and baseline log-transformed level as a covariate. This model will be generated using SAS Proc Mixed with dose group in the CLASS statement and visit in the BY statement. Comparisons of post-baseline log-transformed antibody level will be conducted for each NasoVAX dose group against the placebo group and against the Fluzone group, if applicable. Least square (LS) means and 95% CI of the LS means of dose group, difference of LS means and 95% CI of the difference in LS means will be

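### A single Day 29 HAI requirement gates every primary immunogenicity analysis, and the ITT back-up is not run when one Fluzone subject is the only exclusion

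*SAP*

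**What the plan says.** SAP section 5 (Analysis Populations) gives the PP set priority: "The PP Population is the primary population for immunogenicity analyses". For Fluzone (ALT-FLZ-401) subjects, membership means correct dosing, "and have HAI assay results on Days 1 and 29". ALT-103-201 subjects face the same HAI condition plus the absence of a major deviation. Section 8.6 sets the scope: "All immunogenicity analyses will be conducted on the PP Population". No visit-specific or assay-specific set is defined, and every 14.4.x table and figure in section 10.1 is listed as Per-protocol.

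The ITT set is wider. It takes Safety Population subjects "who have HAI assay results on Day 1 and any postvaccination time point". It is conditional, though. Section 5 states "Analyses based on the ITT Population will be undertaken and presented only if >5% of subjects in any 1 dose group are excluded" from the PP set, and section 8.6 repeats the rule: "only if >5% of subjects in any 1 dose group were excluded from the PP Population". Section 7.4.2 makes Fluzone a dose group of its own and pools the placebo subjects of the three cohorts into one group. Section 4 gives the Fluzone size: "Twenty subjects were enrolled and samples from this study were frozen and stored".

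Three other rules bear on the point. Section 7.4.8 leaves missing results unimputed. Section 7.4.7 assigns early-termination immunogenicity data to the nearest scheduled visit or, if that visit is already filled, to the next one free. Section 8.6 fits the ANCOVA separately for each visit, with baseline as covariate.

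**The concern.** The Day 29 HAI condition acts on the subject, not on the analysis. Results at Days 4, 8 and 15, and the Day 1/Day 8 ELISpot comparison, become conditional on a later, post-vaccination event. A subject who misses only Day 29 also loses the Day 91 and Day 181 titres, in a study whose title names durability. With groups of 15 to 20, each lost subject is 5% to 6.7% of the group.

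The ITT analysis is the natural check on this, since it keeps anyone with a baseline and one later HAI result. At the planned sizes the trigger is met by one exclusion in any group except Fluzone, the active comparator for each NasoVAX dose. If a Fluzone subject is the only exclusion, no planned table shows what the omission did.

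**Working it through.** The 5% trigger is a chosen threshold, so there is no plan figure to reproduce for it.

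**1. What the gate removes.** Take a Fluzone subject with no Day 29 HAI and no sample mapped to Day 29, who attends every other visit. Protocol section 6.3.1 draws HAI blood on Day 1 and on six later days (4, 8, 15, 29, 91, 181). PP then drops:
- five of the six post-baseline HAI results (Days 4, 8, 15, 91, 181);
- the Day 1/Day 8 PBMC pair used for ELISpot;
- the Day 1/Day 29 nasopharyngeal IgA pair, if the Day 29 swab was taken.

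The Day 8 model needs a Day 1 and a Day 8 value. A Day 29 HAI result enters neither it nor the ELISpot comparison.

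**2. When the trigger fires.** The condition is k/n > 5%, with k excluded out of n. Sizes come from SAP sections 4 and 7.4.2: 15 per NasoVAX dose, 3 × 5 = 15 pooled placebo, 20 Fluzone.

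| Group | k/n | Percent | ITT run? |
|---|---|---|---|
| Any NasoVAX dose | 1/15 | 6.7% | yes |
| Pooled placebo | 1/15 | 6.7% | yes |
| Fluzone | 1/20 | 5.0% | no |
| Fluzone | 2/20 | 10.0% | yes |

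The SAP does not state the denominator. With 19, 1/19 = 5.26% would trigger; with 21, 1/21 = 4.76% would not, even if the rule were changed to ≥5%.

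**3. How often the gap opens.** Any one group over 5% brings in the ITT analysis, and nothing limits it to that group. The gap therefore needs exactly one exclusion among 20 Fluzone subjects and none among the other 45 + 15 = 60. Assume independent exclusions at a common rate p, for which the documents give no figure:

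P = 20p(1 − p)^19 × (1 − p)^60 = 20p(1 − p)^79

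- p = 1.25% (the maximum, at p = 1/80): 9.3%
- p = 2%: 0.272 × 0.298 = 8.1%
- p = 5%: 0.377 × 0.046 = 1.7%
- p = 10%: 0.05%

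ALT-103-201 subjects can also leave PP for major deviations. A higher rate among those 60 makes the gap rarer still.

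**4. Size of the effect on a GMT.** If the excluded subject lies d log2 units below the mean of the other 19, the log2 mean with all 20 is lower by d/20. Exclusion therefore multiplies the GMT by 2^(d/20). With d assumed:
- 2-fold below (d = 1): 2^(1/20) = 1.04
- 4-fold below (d = 2): 2^(2/20) = 1.07
- 16-fold below (d = 4): 2^(4/20) = 1.15

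Even the last is 0.2 log2, one fifth of a two-fold dilution step.

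**5. Whether Fluzone subjects are in the back-up set.** ITT sits inside the Safety Population, which section 5 limits to randomized subjects. Section 7.2 says ALT-FLZ-401 needed no randomization. Both definitions name ALT-FLZ-401, so inclusion is plainly intended, but read literally no Fluzone subject qualifies.

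**The case against.** Several points on the other side are sound.

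- **Many early terminators stay in PP.** Protocol section 4.3.2 and footnote g of Table 15.2 send subjects who leave before Day 29 to the Day 29 procedures, which include the HAI sample. If a subject leaves soon after Day 15 and attends that visit, the Day 15 slot is filled and SAP 7.4.7 moves the sample to Day 29. A reader might infer that any Fluzone drop-out disappears from the comparator; the documents do not support that. The mapping does not help a subject lost without a final sample, one who merely misses Day 29, or one whose Day 29 result is unusable. Nor does it help one who leaves soon after Day 8, whose sample would fill Day 15 instead.
- **The arms are not treated differently as a rule.** One exclusion in any 15-subject group brings in ITT for Fluzone too. The asymmetry needs a lone Fluzone exclusion.
- **The data are not lost from the report.** Immunogenicity results go into Listing 16.2.5, and section 8.1 tabulates Safety, ITT and PP counts by group. The omission would be visible, though its effect would not be summarized.
- **The setting is exploratory.** The Fluzone comparison is an exploratory objective, and a PP set with a conditional ITT analysis is a defensible convention. A fixed cohort also keeps the same subjects along the longitudinal plots. This last argument is weaker than it looks: PP fixes only Days 1 and 29, section 7.4.1 removed the Day 15 condition, and nothing is imputed. Denominators at the other visits can already vary.

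**Conclusion.** The point holds at minor severity. The Day 29 HAI gate has no analytic purpose for other visits or for ELISpot, and it applies in every group. Even when ITT is triggered, the primary tables still omit the affected subjects' valid data.

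The trigger gap is real but narrow. It rests on a denominator of 20 and on one Fluzone subject being the only exclusion in either study. Its probability is at most 9.3% under a common independent exclusion rate, and below 2% once that rate reaches 5%. The assumed GMT shifts run from 1.04 to 1.15. Nothing in the documents shows that such an exclusion occurred, or that any comparison would change. A reader might infer a biased Fluzone comparison; neither the text nor the arithmetic supports that.

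**What to change.** In SAP sections 5 and 8.6:

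1. Present the ITT immunogenicity analysis unconditionally and delete the 5% trigger. Changing it to ≥5% would cover 1/20 but would fail again at 1/21.
2. Reword the Safety and ITT definitions so that the non-randomized Fluzone subjects are included, for example *randomized or, for ALT-FLZ-401, enrolled*. Without this, removing the trigger does not, read literally, bring them into the back-up set.
3. Apply the Day 29 HAI condition to Day 29 HAI endpoints only. For each other visit and assay, include correctly dosed subjects with no excluding major deviation who have a baseline and that visit's result for that assay.

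The cost is SAP wording and one more run of existing programs. The downside is that denominators will differ by visit and assay, so each table and figure must show its own n.

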6.1 Study Drug Dosing

- Vaccine administered
- Treatment dose

6.2 Demographics and Baseline Characteristics

- Sex
- Age
- Race
- Ethnicity
- Weight
- Height
- Body mass index (BMI)
- Medical/surgical history
- Prior medications

6.3 Endpoints

Primary, secondary, and exploratory endpoints are listed in Section 3.

6.4 Safety Variables

Safety assessments, some of which are listed as endpoints, include the following:

- Reactogenicity (local events, systemic events, and oral temperature)
- AEs and SAEs (events not already included in reactogenicity)
- Safety laboratory tests (hematology, serum chemistry, urinalysis)
- Vital signs (blood pressure, heart rate, body temperature)
- ECG
- Nasopharyngeal swabs for vector shedding
- Viral culture
- Concomitant medications
- Physical exam

7 Statistical Methodology

7.1 Sample Size

The sample size for ALT-103-201 was selected as adequate and reasonable for an initial review of the safety and immunogenicity profile of the NasoVAX at doses to be well tolerated by young adults, rather than for statistical power. The sample size will permit initial estimates of reactogenicity. Given a total of 45 subjects receiving NasoVAX, the study will have an 80% probability of detecting at least 1 AE which occurs at a rate of 3.6%. If no SAEs are observed among the 45 subjects who receive NasoVAX, an approximation to the 1-sided upper bound of the 90% CI on the rate of SAE occurrence would be 5%.

Approximately 60 subjects will be enrolled in ALT-103-201.

The sample size for ALT-FLZ-401 was 20 healthy subjects; this size was based on practical considerations.

7.2 Randomization

ALT-103-201 Subjects will be enrolled into 3 sequential cohorts of 20 subjects each defined by the viral particle dose (1×10^9 , 1×10^{10} , or 1×10^{11} vp). Within each sentinel group and cohort, subjects will be randomized at a ratio of 3:1 ratio to receive 1 intranasal dose of NasoVAX or placebo on Day 1.

A sentinel cohort of 5 subjects from each cohort will be dosed. Dosing of the remainder of each cohort may proceed after the last sentinel subject completes Day 8 if no events meeting stopping criteria (Section 6.6 of the ALT-103-201 protocol) have occurred. The SRC, consisting of the Investigator, the Medical Monitor, and a Sponsor Representative, will review all AE, reactogenicity, and laboratory data through Day 8 for all subjects in each cohort before subjects are randomized to the next higher dose.

No randomization was required for the ALT-FLZ-401 study.

7.3 Interim Analysis

One interim analysis of humoral immunogenicity data (including summaries of antibody levels measured by HAI and influenza MN in serum) and safety data (including summaries of AE, reactogenicity, concomitant medications and vaccines, vital signs, ECG, and safety laboratory data and listing of any viral culture results) will be conducted when all clinical data through the Day 29 visit is available and monitored for all subjects. The purpose of this review is to plan future studies and adjust the clinical development plan accordingly.

The study and sponsor's biostatisticians and statistical programmers will be unblinded when all clinical data through the Day 29 visit are collected and cleaned, and will

perform the interim analysis. Other study personnel, including Investigators and investigational site staff, Sponsor staff, and contractors, will remain blinded to individual treatment assignments until database lock for final analysis.

Safety and immunogenicity analyses from the interim review may be presented in an interim statistical report drafted by the Sponsor. Data therein will be used to support development and planning of future studies, and may be submitted to the Center for Biologics Evaluation and Research and other Regulatory Authorities as needed.

7.4 Analysis of the Study

All statistical tests will be two-sided and a difference resulting in a p-value of less than or equal to 0.05 will be considered statistically significant. All p-values will be rounded to and displayed in four decimals. If a p-value less than 0.0001 occurs it will be shown in tables as <0.0001.

There will be no multiplicity adjustments.

To integrate the 2 studies for the immunogenicity tables, figures, and listings (TFL), subjects enrolled in ALT-FLZ-401 will be treated as an additional arm in the ALT-103-201 study. ALT-FLZ-401 subjects will be denoted as "Fluzone" subjects in the TFL, while ALT-103-201 will be denoted as "NasoVAX" if they are assigned to an active dose, or placebo if appropriate.

Descriptive summaries of variables will be provided where appropriate. Continuous variables will be presented for each dose group by geometric means and 95% confidence intervals (CIs) for the immunogenicity endpoints and by summary statistics (e.g., mean, and standard deviation [SD], median, minimum, and maximum) for other endpoints. Categorical variables will be presented by frequency distributions (including percentages and 95% CIs) for the immunogenicity endpoints and frequency counts and percentages for other endpoints. Expansion of descriptive table categories within each dose group may occur if such elaborations are thought to be useful.

All collected data will be presented in listings. Data not subject to analysis according to this plan will not appear in any tables or graphs but will be included in the data listings.

Post-hoc exploratory analyses not identified in this SAP may be performed to further examine the study data. These analyses will be clearly identified as such in the final clinical study report.

7.4.1 Changes in Analysis in Comparison to Study Protocol

The PP population definition was modified to remove the requirement of having HAI assay results at Day 15. Otherwise, the analyses described in this analysis plan are consistent with the analyses described in the study protocols.

7.4.2 Study Data

For all summaries and analysis, ALT-103-201 subjects who are randomized to and/or treated with placebo from each of the 3 cohorts will be pooled into a single group.

Study data from the ALT-103-201 study will be integrated with data from the ALT-FLZ-401 in the analysis datasets; ALT-FLZ-401 will be treated as a separate dose group from the 4 arms of the ALT-103-201 study.

Study data identified in the schedule for time and events (Table 4-2) are collected, and source verified, on the electronic data capture (EDC) product Viedoc Clinic (Version 4.36) for the ALT-103-201 study, and on the ClinPlus Data Management System (3.3 SR2) for the ALT-FLZ-401 study. For the ALT-103-201 study, safety laboratory tests and viral culture are provided by ACM; the specialty laboratory vendors for tests that are not collected in the EDC tool are Altimmune UK (PBMC ELISpot), MPI (qPCR lab data [nasopharyngeal swab]), Battelle (Ad5 lab data [serum]), and Southern Research Institute (HAI and influenza MN [serum], and IgA lab data [nasopharyngeal swab]). For the ALT-FLZ-401 study, the Southern Research Institute will also be used for HAI, influenza MN, and IgA lab data; the analysis of these humoral response lab data will be completed simultaneously for both studies. The ALT-FLZ-401 study will also use Altimmune UK for the analysis of PBMCs, which will be completed simultaneously for both studies. Analysis of IgA lab data may be completed by a different specialty laboratory which will be determined prior to the end of the study. Samples which are being analyzed for both studies are pooled so that the lab will not know from which the study the sample was taken.

All study data will be formulated into regulatory compliant data sets to provide transparency, traceability, and integrity of trial analysis results from the collection source. Observed study data will be mapped to the CDISC Study Data Tabulation Model (SDTM) and serve as the source data from the trial. All study analyses will be completed using analysis data sets that are derived from the SDTM and follow the CDISC Analysis Data Model (ADaM) architecture. All planned analyses will be performed using the ADaM data sets developed for this study.

